6. STUDY PROCEDURES

Overall approach: A total of 3 study visits are planned (**Table 1**) The first visit is the baseline visit, and the other two are double-blind placebo-controlled medication visits, where either CBD or placebo will be administered. Participants will be randomized using a random-number generator in a 1:1 ratio of CBD to placebo. During the baseline visit, after obtaining informed consent, participants will complete the baseline assessments. The subject will then be scheduled for their study visits 2 and 3 during which they will receive CBD or placebo in random order in double-blind fashion. Visits 2 and 3 will be scheduled at

Research Consent Form**General Consent Form Template****Version Date: February 2021**

Subject Identification

least 1 week apart to function as a washout. Baseline visit will take no longer than an hour, and the subsequent visits will take no more than 2 hours to complete.

Visit 1: Baseline

Participants will provide written informed consent, obtained by the PI or another study physician. The blood and urine samples collected during the Baseline Visit will be used for inclusion/exclusion purposes. Specifically, participants who are currently pregnant (as confirmed by the pregnancy test), or have hepatic liver enzymes greater than three times the upper normal limit (as confirmed by the liver function tests, or LFTs) will be excluded. Subjects will also complete baseline PHQ9, GAD7, BPI, TLFB, COWS, PANAS, and opioid cravings.

Visit 2: CBD or placebo

After arrival to the study site, the participant will receive either the CBD 600mg or placebo, immediately followed by obtaining baseline heart rate, blood pressure, PHQ9, GAD, BPI, TLFB, COWS, opioid cravings, and urine sample for toxicology testing. Heart rate and blood pressure will be monitored every 30 minutes (vital signs: heart rate, blood pressure) following receipt of CBD or placebo. At 60 minutes following the CBD or placebo administration, the participant will then proceed to complete the cue-reactivity test, visual probe task, Iowa gambling task, monetary choice questionnaire (MCQ), and the mirror tracing persistence task (MTPT). Just prior to and after the MTPT task, subjects will provide saliva sample and complete the positive and negative affect scale (PANAS). An additional saliva sample will be collected 20 minutes after the MTPT task.

Visit 3: CBD or placebo

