The same procedures for Visit 2 will be repeated during visit 3, scheduled at least 1 week after visit 2. The order in which CBD or placebo is administered will be randomized.

Cannabidiol:

Research Consent Form

General Consent Form Template

Version Date: February 2021

Subject Identification

Subjects will receive 600mg of oral CBD or matching placebo. Cannabidiol will be provided using Epidiolex™ oral solution 100mg/mL. Drug will be procured by the BWH Investigational Drug Services (IDS) pharmacy and the pharmacy at Rutland Regional Medical Center. The CBD or matching placebo will be placed in oral syringes for the subjects to self-administer at the study site. CBD will be stored at room temperature (68 to 77 F) in its original bottle and in an upright position. Once opened, CBD has a shelf life of 84 days.

Primary Outcome: The primary outcomes is the change in cue-induced cravings (Opioid Craving Scale).

Secondary Outcomes: The secondary outcomes are impulsive decision making (Iowa Gambling Task, Monetary Choice Questionnaire), attentional bias (Visual Probe Task), and physiologic and subjective stress-reactivity.

Assessments:

- Patient Health Questionnaire 9-item (PHQ9): Assessment of depressive symptoms
- Generalized Anxiety Disorder 7-item (GAD7): Assessment of anxiety symptoms
- Brief Pain Inventory (BPI): Pain severity and interference assessment.
- Time-line follow back (TLFB): A method of assessing for recent substance use using a calendar.
- Clinical Opioid Withdrawal Scale (COWS): Assessment of opioid withdrawal.
- Opioid craving scale¹²: A 3-item tool to assess current cravings, cravings when exposed to triggers, and likelihood of using if placed in an environment that the individual previous used opioids.
- Cue-induced craving¹³: Participants will be shown both illicit opioid-related and neutral images on a computer screen for one minute each using a standardized protocol. The order in which the cues will be presented will be randomized and counter balanced. Participants will rate their cravings on a visual analog scale. The cue exposure procedure will end with a standardized debriefing exercise. It is important to note that cue-exposure is a safe paradigm for studying craving in this population when employing debriefing procedures.

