- Monetary Choice Questionnaire (MCQ)¹⁴: This is a 27-item self-report tool used to measure delayed discounting, or the degree to which individuals prefer smaller immediate rewards compared to larger delayed rewards. Participant are asked to choose between a smaller (in dollars) immediate reward and a larger delayed reward.

Study visit number	1	2	3
Informed consent	X		
Pregnancy test	X		
Liver Function Test	X		
Urine toxicology	X	X	X
Heart rate, blood pressure	X	X	X
PHQ9	X	X	X
GAD7	X	X	X
BPI	X	X	X
TLFB	X	X	X
COWS	X	X	X
PANAS	X	X	X
Opioid Cravings	X	X	X
Cue- and stress-reactivity	X	X	
Visual Probe Task	X	X	
Iowa Gambling Task	X	X	
Monetary Choice Questionnaire	X	X	
CBD 600mg or Placebo	X	X	
Adverse effects	X	X	

Table 1: Schedule of assessments

PHQ-9=Patient Health Questionnaire; GAD7=Generalized Anxiety Disorder 7; BPI=Brief Pain Inventory; TLFB=Time-Line Follow Back; COWS=Clinical Opioid Withdrawal Scale; PANAS=Positive and Negative Affect Schedule

Research Consent Form

General Consent Form Template

Version Date: February 2021

Subject Identification

- Iowa Gambling Task (IGT)¹⁵: This is a task to measure decision making, which utilizes four decks of cards (A, B, C, D). Participants are instructed to maximize profits by selecting cards from any deck. Cards from decks A and B earn more profits but lead to even higher occasional losses leading to net long-term losses, while decks C and D yield low profits but only low occasional losses resulting in a net long-term profit.
- Visual Probe Task¹⁶: Opioid-related and neutral images will be used. Each trial will begin with a fixation point lasting 500ms. A pair of images then will appear on the left and right of the screen for either a short (200ms) or long (500ms) stimulus duration to assess automatic orientating and controlled attention processing, respectively. Image pairs will be replaced by a probe in the location of either the opioid-related or neutral image. The probe will remain until the participant responds to identify the probe orientation by pressing the response keys as quickly as possible.

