- Impulsive decision making: A net score from the IGT is calculated by subtracting the number of disadvantageous selections from the number of advantageous selections (i.e. (C+D) - (A+B)), where negative scores indicate decision-making that favors immediate rewards despite negative consequences.

Research Consent Form

General Consent Form Template

Version Date: February 2021

Subject Identification

- Distress tolerance: This is measured as the length of time in number of seconds that participants engage in the third MTPT task.
- Subjective stress reactivity: Subjective stress reactivity will be calculated as the difference in the negative affect score from PANAS before and after the stressor task.
- Physiologic stress reactivity: Physiologic stress reactivity will be calculated as the difference in salivary cortisol levels and skin conductance before and after the stressor task.

Power analysis: The estimated mean change in cue-induced cravings scores from prior studies is -1.5 (SD 1.5). Based on this estimate, and a conservative estimate of a correlation of $r=0.60$ between the two time points, a sample size of 10 is needed for 88% power and two-tailed alpha set at 0.05 for a paired-samples t-test. A point estimate of the difference in the change and the 95% confidence interval will be reported. Conversely, if the change in cravings is not normally distributed, then a sum rank test will be used.

10. Monitoring and Quality Assurance

INSTRUCTIONS

Delete grey Instructions box upon completion of this section

Describe the plans that will be followed by study staff for monitoring and quality assurance, including:

- Adverse event criteria and reporting procedures
- Planned safety monitoring, e.g., data monitoring committee (DMC)/data and safety monitoring board (DSMB), independent monitor, PI-monitored, etc., including planned frequency of review. If DMC/DSMB monitored, include either charter as separate attachment or complete DMC/DSMB [APPENDIX](#)
- Outcomes monitoring, including planned frequency of review.
- Study stopping rules as applicable
- Internal monitoring of source data, protocol adherence, and recordkeeping, including which staff will be responsible and planned frequency of review
- Independent monitoring of source data as applicable

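### The Iowa Gambling Task is repeated at Visit 3 with no alternate form and no period term, so deck knowledge from Visit 2 can blur or bias the CBD–placebo contrast on this secondary outcome

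*Combined protocol and SAP*

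**What the plan says.** Section 6 (Visit 2) has participants, 60 minutes after CBD or placebo, "complete the cue-reactivity test, visual probe task, Iowa gambling task, monetary choice questionnaire (MCQ), and the mirror tracing persistence task (MTPT"). For the second drug visit it says: "The same procedures for Visit 2 will be repeated during visit 3, scheduled at least 1 week after visit 2". The gap is described only as "least 1 week apart to function as a washout", and "The order in which CBD or placebo is administered will be randomized".

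Section 6 (Assessments) describes the IGT decks once, with no version for each visit: "Cards from decks A and B earn more profits but lead to even higher occasional losses leading to net long-term losses", whereas "decks C and D yield low profits but only low occasional losses resulting in a net long-term profit". Section 9 (Impulsive decision making) gives one score for the task, obtained by "subtracting the number of disadvantageous selections from the number of advantageous selections (i.e. (C+D) - (A+B")). The task's status is also set in Section 6: "The secondary outcomes are impulsive decision making (Iowa Gambling Task, Monetary Choice Questionnaire").

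Allocation is 1:1 by random-number generator, with no blocking stated (Section 6, Overall approach). Section 9 analyses every comparison by a paired t-test or a non-parametric test, with no period, sequence or carry-over term. Neither section mentions an alternate IGT form, re-mapped or re-sequenced decks, or a practice session. By contrast, for the cue images Section 6 does provide for random, counterbalanced presentation order.

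**The concern.** A participant finds out which IGT decks pay by winning and losing on them, and the score counts choices from the paying decks. Knowledge kept from Visit 2 therefore feeds directly into the Visit 3 score. A gap meant to clear a drug is not designed to clear that knowledge.

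There are two separate consequences:

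- **Common learning.** If everyone improves by the same amount at Visit 3 whatever came first, the CBD–placebo difference moves down in CBD-first participants and up in placebo-first participants. This spreads out the paired differences. If the two orders are unequal in size, it also shifts their mean.
- **Learning that interacts with treatment.** If CBD improves what is learned at Visit 2, the CBD-first group takes that gain into its placebo visit. If knowing the decks leaves less room for CBD to act, the placebo-first group shows a smaller effect at its CBD visit. Either one changes the expected contrast itself.

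Decision making appears in the aim, the hypothesis and the secondary outcomes. As planned, a null IGT result could not distinguish no effect of CBD from an effect hidden by learning.

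**Working it through.** **The plan's own power figure.** Section 9 gives a mean change of −1.5, SD 1.5, r = 0.60, N = 10 and two-sided alpha 0.05, all for craving. SD of the paired difference = 1.5 × √(2 × (1 − 0.60)) = 1.342. Standardised effect = 1.5/1.342 = 1.118. The noncentral t with 9 degrees of freedom gives power 0.881, which matches the stated 88%. No effect size, SD or power is given for the IGT.

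**Model for the IGT.** D is the CBD effect in a participant new to the task. p is the Visit 3 learning gain common to both orders. f is the share of D lost once the decks are known. g is the share of the extra learning under CBD that is retained into the placebo visit. The documents give none of these. Expected CBD minus placebo:

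- CBD first: D − p − gD
- Placebo first: D(1 − f) + p
- Average of the two orders: D(1 − (f+g)/2)

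The common gain p cancels in that average; f and g do not. At f+g = 0.5 the result is 0.75D, and at f+g = 1 it is 0.50D. At f = −0.5, g = 0 (a CBD effect that grows with task knowledge) it is 1.25D.

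**The planned analysis in one trial.** With n1 CBD-first and n2 placebo-first participants out of 10, the unadjusted paired mean has expectation

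D(1 − (n1·g + n2·f)/10) + p(n2 − n1)/10.

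If allocation is simple randomization, an exact 5:5 split has probability 252/1024 = 24.6%, and 7:3 or worse has 352/1024 = 34.4%. With f = 0 and g = 0.5:

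- 7 CBD first: 0.65D − 0.4p
- 3 CBD first: 0.85D + 0.4p, which exceeds D when p > 0.15D/0.4 = 0.375D

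**Illustrative power.** This borrows the craving effect of 1.118 for the IGT, with p in units of the SD of the paired difference, a 5:5 split and 40,000 simulated trials per case.

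*Common learning only (f = g = 0).* The mean estimate stays at 100% of D. The learning gain raises the variance of the ten differences from 1 to about 1 + (10/9)p², so the SD is √2.11 = 1.45 at p = 1 and √5.44 = 2.33 at p = 2.

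| p | Paired t-test | With period term |
|---|---|---|
| 0 | 0.88 | 0.87 |
| 0.5 | 0.82 | 0.87 |
| 1 | 0.60 | 0.87 |
| 2 | 0.08 | 0.87 |

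*Learning that interacts with treatment.* With a period term in the model, power is about 0.64 at f+g = 0.5 and about 0.34 at f+g = 1. The mean estimate is 75% and 50% of D, with or without that term.

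**Fallback after the fact.** Comparing Visit 2 only, 5 against 5, at a difference of 1 SD has no carry-over but power of only about 0.29.

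**The case against.** The documents do not say that the decks are identical at Visit 3. Repeating the procedures need not mean the same screen positions or card order, and the letters in the score could label deck types. That stands as a limit on the claim: what is supported is that no alternate form is specified. An unchanged mapping is still the natural reading, given one deck description and one fixed-letter formula. If the letters denote fixed positions, that formula would mis-score a re-mapped visit.

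Section 9 also reads a negative score as favouring immediate reward. If CBD acts on that preference and not on learning, treatment-dependent carry-over of knowledge need not arise. This too stands: g may be zero, and the documents give no retention figure.

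A reader might infer that repeating the task must shrink any CBD effect. The documents do not support that. Equal learning leaves the expected effect unbiased, shrinkage needs f+g above zero, the opposite direction is possible, and an unbalanced split can push a single unadjusted estimate either way. A reader might also infer that a period term is of no use. In fact it removes the common part of learning, and the plan has no such term.

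Finally, the sample of 10 was sized for craving, so a null IGT result would be weak evidence in any case. That limits the importance of the point but is no reason to leave an avoidable source of error in place.

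**Conclusion.** The concern holds in conditional form. As written, the plan does nothing to limit deck knowledge carrying from Visit 2 to Visit 3 beyond a gap intended as a drug washout. Common learning costs precision, and in an unbalanced split adds a shift of p(n2 − n1)/10; a period term would remove both. Learning that depends on the first treatment, or an effect blunted by experience, would bias the contrast by a factor of 1 − (f+g)/2, and neither washout nor a period term repairs that. Attenuation of 25% to 50% corresponds to f+g between 0.5 and 1. That range is assumed, and the direction is plausible, not established. The power figures also rest on borrowing the craving effect size.

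Only the IGT, a secondary outcome, is affected. Nothing here touches the primary craving outcome or its 88% power. This is a worthwhile, inexpensive improvement and not a flaw in the trial's main comparison.

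**What to change.** - Prepare two parallel IGT forms that differ in which decks are advantageous and in card sequence. Give one at each drug visit, with form order counterbalanced across treatment order.
- In Section 9, define the score as advantageous minus disadvantageous selections under the mapping used at that visit, in place of the fixed letters.
- Add a period term to the IGT comparison.
- If a parallel form is already intended, say so in Section 6 and align the score with it.

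The cost is task configuration and a few sentences in Sections 6 and 9, with no extra visit, staff or participant time. The period term uses one degree of freedom: in the illustration with no learning, power goes from 0.88 to 0.87 with a 5:5 split, or to 0.83 under simple randomization.

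Two downsides remain. General insight that some decks are bad will survive a change of form. Crossing two form orders with two treatment orders also gives four cells of two or three participants each, so differences between forms add some noise. The change has to be made before Visit 3 data are collected, because a later Visit 2-only analysis would have little power.

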Adverse reactions to study procedures: The study procedures will end with a standardized relaxation and debriefing exercise. Before participants are discharged from each study session, their well-being will be assessed by the study staff and a standardized safety and adverse events questionnaire will be used to assess any adverse events. If needed, participants will be referred for further clinical evaluation and assistance. It is important to note that cue-exposure and stress-exposure are safe paradigms for studying this patient population when employing debriefing procedures.

Suicidal ideation: Patients with OUD frequently have psychiatric co-morbidities, namely depression. Participants who disclose any suicidal ideation during the study (either through spontaneous expression of suicidal ideation, or self-reported on the PHQ-9) will result in emergent evaluation by a licensed clinician member of the study staff for appropriate assessment and triage. Any disclosures will be handled within existing legal mandates, clinical practice, and social norms. Consistent with standard clinical practice, when possible, disclosures will be discussed with the participant to determine the best management options. This may include notifying the outpatient providers or family members, referring to medical treatment, calling emergency services, or escorting the participant to the Emergency Room at Brigham and Women's Hospital. When required by law, the police department will be notified. The candidate is a board certified psychiatrist and has extensive experience managing acutely distressed patients with mental or substance use disorders.

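### At Visits 2 and 3 the product is given before that day's PHQ9 and adverse-event questions, so those answers cannot inform the decision to dose

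*Combined protocol and SAP*

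**What the plan says.** Section 6, Visit 2, sets the order on arrival: "the participant will receive either the CBD 600mg or placebo, immediately followed by obtaining baseline heart rate, blood pressure, PHQ9, GAD", followed by the remaining questionnaires and a urine sample. Visit 3 follows suit: "The same procedures for Visit 2 will be repeated during visit 3, scheduled at least 1 week after visit 2". Testing begins an hour after the dose: "At 60 minutes following the CBD or placebo administration, the participant will then proceed to complete the cue-reactivity test".

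Section 7, under adverse reactions to study procedures, puts the safety check at the end of the session: "Before participants are discharged from each study session, their well-being will be assessed by the study staff", and in the same sentence "a standardized safety and adverse events questionnaire will be used to assess any adverse events". Under suicidal ideation, the same section says that ideation disclosed spontaneously "or self-reported on the PHQ-9) will result in emergent evaluation by a licensed clinician member of the study staff".

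Table 1 lists the PHQ9 and adverse effects by visit but gives no order within a visit. Section 4 uses the PHQ9 for eligibility at baseline only, excluding scores above 10.

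**The concern.** Section 7 names suicidality among the possible side effects of CBD and makes a PHQ9 report of ideation a trigger for urgent assessment. The protocol therefore collects the relevant answer at each dosing visit, but only after the product has been swallowed. A participant who arrives with new ideation, or with an unresolved symptom that nobody has asked about, is dosed first and evaluated second. This can precede a CBD dose at Visit 2 for those randomized to CBD first, and at Visit 3 for those randomized to placebo first. Staff are blinded and cannot tell which visit carries the CBD, so the question arises at both.

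What is at stake is a participant-safety decision made without information that the plan already intends to gather. The efficacy analysis is not affected.

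**Working it through.** **The plan's own figure.** The plan gives no number on dosing order. Its one design figure is the power in Section 9, from a mean change of -1.5, SD 1.5, r = 0.60, n = 10 and two-sided alpha 0.05:

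- SD of the paired difference = 1.5 × √(2 × (1 − 0.60)) = 1.342
- standardized effect = 1.5 / 1.342 = 1.118
- noncentrality = 1.118 × √10 = 3.536, with 9 degrees of freedom
- power = 88.1%, against 88% stated

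The figure reproduces, and none of its inputs depends on dosing order. The PHQ9 is not among the outcomes listed in Section 9, so moving it changes no endpoint.

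**Order within a dosing visit (Sections 6 and 7).** Arrival; product; vital signs, PHQ9 and other measures; tasks from 60 minutes; last saliva sample 20 minutes after the stress task; adverse-event questionnaire before discharge.

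**What is on hand when the product is released.**

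| Decision | Latest PHQ9 | Latest scheduled adverse-event question |
|---|---|---|
| Visit 2 dose | Visit 1; the gap to Visit 2 is not stated | At most one at the end of Visit 1, if the baseline visit counts as a session |
| Visit 3 dose | Visit 2, at least 7 days old | Visit 2 discharge, at least 7 days old |

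The gap is therefore that day's PHQ9, plus any event that began since the previous visit and was not volunteered.

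**Search for a pre-dose check elsewhere.**

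- Section 7, on cannabidiol safety, describes monitoring during and after administration. Its sentence breaks off in the text available.
- Section 10 has weekly meetings that review side effects already reported. They do not prompt a question to the participant.
- The stopping rules concern ending the study, not withholding one person's dose.
- The study schema figure is not shown.

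Nothing in the available text puts a safety question before the dose.

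**Count.** 10 participants × 2 visits = 20 administrations, of which 10 are CBD and 10 placebo. Each participant takes CBD once. This counts decisions made without the answers. It is not a risk estimate, and the documents give no rate from which to make one.

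**Time cost of reordering.** Assume 5 to 10 minutes for both forms and their review, since form length is not stated. A visit is capped at 120 minutes, testing starts 60 minutes after the dose, and the last saliva sample is 20 minutes after the stress task:

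- time left for the five tasks = 120 − 60 − 20 = 40 minutes
- share taken by the delay = 5/40 = 12.5% to 10/40 = 25%
- time then left = 35 to 30 minutes
- total over the trial = 20 × 5 = 100 to 20 × 10 = 200 minutes

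The 40 minutes is an upper figure. It assumes that dosing takes no time after arrival and that the debriefing and discharge questionnaire fit inside the 20-minute saliva wait.

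**The case against.** The strongest reply is that little can go wrong. Each person receives one CBD dose and nobody is re-exposed. Baseline screening has already excluded higher PHQ9 and GAD7 scores and raised liver enzymes. Section 7 cites an earlier pilot that gave this dose for three days, and two randomized studies that it describes as free of adverse effects. The PHQ9 follows the dose at once, on site, and a report of ideation still brings a clinician during the visit. All of this stands and is why the point is minor. It does not alter the fact that the answer arrives too late to affect that dose.

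It can also be said that the protocol never makes the PHQ9 at Visits 2 and 3 a condition for dosing. That is correct: the change adds a safeguard and does not repair a broken rule. If calling these measures baseline was meant to imply that they come before the dose, the written order should say so.

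Three stronger readings are tempting, and the documents do not support them.

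- A reader might infer that no adverse-event information at all precedes the Visit 3 dose. It does: the Visit 2 discharge questionnaire and the weekly meetings come first.
- A reader might take all 20 administrations as the exposure at risk. Ten are placebo, and an event caused by CBD cannot be followed by a second CBD dose.
- A reader might infer that late events cannot be dated or attributed to a period. The questionnaire's content is not shown, and it may already record onset. Events after Visit 3 discharge are a separate matter that reordering would not touch.

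**Conclusion.** The point holds in limited form. At both dosing visits, that day's PHQ9 ideation answer cannot inform the decision to dose. The same is true of any unvolunteered event that began since the last study visit, which for Visit 3 means after Visit 2 discharge. It concerns 10 single CBD doses at low absolute risk, with no effect on the primary endpoint, sample size or power.

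The conclusion rests on reading the Section 6 sequence literally, and on the missing schema and the truncated sentence in Section 7 not containing a pre-dose check. If either does, the remedy reduces to making Section 6 agree with it. This is a cheap improvement of minor weight.

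**What to change.** In Section 6, with a timing note in Table 1, have staff give and review the PHQ9 and the existing adverse-event questions on arrival at Visits 2 and 3, before the product is released. Keep the discharge questionnaire. Both visits are needed because of the blinding.

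- If suicidal ideation is reported, complete the clinician evaluation already described in Section 7 before dosing.
- If an unresolved event concerns the study physician, postpone the visit. The washout rule sets a minimum of one week and no maximum, so postponement fits the protocol.

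No new form or staff role is required, and the 60-minute interval from dose to testing is unchanged. The cost is a short paragraph of text, the assumed 5 to 10 minutes before each dose, and an occasional postponed visit. Because the time for tasks is already tight, the 2-hour limit may need an allowance of up to 10 minutes so that the delay does not shorten the outcome assessments.
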